## **Secondary Efficacy Endpoints**

The categorical secondary efficacy endpoint of maintaining  $HbA_{1c}$  <7.0% (and  $HbA_{1c}$  <6.5% and  $HbA_{1c}$  <7.5%) will be analyzed longitudinally using a generalized linear mixed model in the FAS population. The model will include the fixed, categorical effects of treatment, stratification factors (ie, background AHA and age group), visit, and treatment-by-visit interaction, as well as the fixed, continuous covariates of baseline and baseline-by-visit interaction. An unstructured covariance will be used to model the within subject errors. The odds ratio and 2-sided 95% CI for the treatment comparisons at Week 26 (canagliflozin compared to placebo) will be estimated based on this model.

Continuous endpoints (except for triglycerides) will be analyzed with an MMRM model described before in the FAS population. For the endpoints with post-baseline assessments taken only at Week 26 and Week 52, an ANCOVA model similar to the primary efficacy endpoint will be used at Week 26. The least-squares means for the treatment comparisons and their 2-sided 95% confidence intervals will be estimated based on this model. The analysis of percent change in triglycerides may be based on nonparametric methods (given the anticipated skewed nature of this parameter) or alternative methods, to be further described in the SAP.

## TIME AND EVENTS SCHEDULE

	Pret	reatment Ph	ase											
	Screening Visit	2-week SB PBO Run-In	Baseline		Double-blind Treatment Phase a								Post- treatment	
	Wk -3	Wk -2 b	Day 1	Wk 3 TC	Wk 6	Wk 12	Wk 13°	Wk 20	Wk 26	Wk 34	Wk 42	Wk 52/EOT /Early Withdrawal d	Rescue Visit	Telephone call at Wk 56 or 30 days post last dose e
Screening/Administrative														
Informed consent	Xf													
Child or adolescent assent	$X^{f}$													
Inclusion/Exclusion criteriag	X	X	X											
Medical history and demographics	X													
Prestudy therapyh	X													
Concomitant therapyi	X	X	X	X	X	X		X	X	X	X	X	X	
Randomization			X											
Assess eligibility for re- randomization j						X								
Re-randomization of eligible subjects							Xc							
Study Drug Administration	n													
Dispense single-blind placebo		X												
Assess for single-blind placebo compliance			X											
Dispense double-blind study drug			X		X	X	$X^k$	X	X	X	X			
Drug Accountability					X	X	X	X	X	X	X	X	X	
Assess/Reinforce double- blind study drug compliance				Х	X	х	X	X	Х	X	X		Х	
Review thresholds for potential need for rescue medication 				х	X	X		X	X	X	X		X	

	Pret	reatment Ph	ase											
	Screening Visit	2-week SB PBO Run-In	Baseline		Double-blind Treatment Phase a								Post- treatment	
	Wk -3	Wk -2 b	Day 1	Wk 3 TC	Wk 6	Wk 12	Wk 13°	Wk 20	Wk 26	Wk 34	Wk 42	Wk 52/EOT /Early Withdrawal d	Rescue Visit	Telephone call at Wk 56 or 30 days post last dose e
Clinical Procedures														
Vital signs m	X		X		X	X		X	X	X	X	X	X	
Body weight n	X		X		X	X		X	X	X	X	X	X	
Height o	X		X		X	X		X	X	X	X	X	X	
Tanner Staging p			X						X			X	X	
Physical examination q			X						X			X	X	
Subject Counseling and On	ngoing Revie		nts											
Diet/exercise counseling r		X												
Diet/exercise monitoring and re-enforcement			X	X	X	X		X	X	X	X	X	X	
Counseling for						+				$\vdash$	-	-		
hypoglycemia and recognition & treatment of ketosis-related medically		X	x	X	X	X		X	X	х	x		х	
important events r Review of subject diary s			X	X	X	X		X	X	X	X	X	X	
Record hypoglycemic episodes t and ketone levels		X	X	X	X	X		X	X	X	X	X	X	
Dispense glucose/ketone meter & test strips, urine ketone strips, and subject diary (as needed) u		X	X		х	х		X	X	X	X		х	
Safety Evaluations														
Foot examination v			X						X			X	X	
Record adverse events w		X	X	X	X	X	X	X	X	X	X	X	X	Xe
Laboratory Assessments														
Fasting plasma glucose x			X						X			X	X	
Hemoglobin A 1c	X		X		X	X		X	X	X	X	X	X	
Site fingerstick glucose			X											
Random C- peptide	X													
Fasting C-peptidex			X		 				X			X	X	
Hematology y	X		X						X			X		
Serum chemistry panely	X		X			X			X			X	X	

	Pret	reatment Ph	ase	 										
	Screening Visit	2-week SB PBO Run-In	Baseline		Double-blind Treatment Phase a									Post- treatment
	Wk -3	Wk -2 b	Day 1	Wk 3 TC	Wk 6	Wk 12	Wk 13°	Wk 20	Wk 26	Wk 34	Wk 42	Wk 52/EOT /Early Withdrawal d	Rescue Visit	Telephone call at Wk 56 or 30 days post last dose e
Blood ketones			X			X			X			X		
Fasting serum lipid profile x,y			X						X			X		
Urinalysis y			X									X		
Serum pregnancy test z	X													
Urine pregnancy test z									X			X		
First morning void urine for Urinary albumin/creatinine ratio aa,bb,cc		$X^{cc}$							Xcc			Xcc		
GAD and islet cell antigen 2 [IA2] antibody test dd	X													
Pharmacokinetic Evaluation	ons													
Pharmacokinetics blood sample ee						X			X			X		
Bone turnover markers (serum osteocalcin and serum collagen type 1 carboxy-telopeptide [CTx])			х						X			х		
Markers of calcium and phosphate homeostasis (calcium, magnesium, phosphate, parathyroid hormone (PTH), 25- hydroxy Vitamin D, calcitonin; urinary excretion of calcium and phosphate)			х						х			х		
Archived sample (plasma, serum, and urine samples) for exploratory analyses x			X						X			X		

Key: EOT= end-of-treatment; Wk= week; SB PBO= single-blind placebo; TC= telephone contact

- a. All visits will be scheduled based on the date of randomization (Day 1). The study visits should generally occur within a 7-day recommended window (ie, ±7 days) around the protocol-specified visit schedule during the double-blind treatment phase. There may be exceptional cases where it is possible, with the concurrence of the sponsor's medical monitor, that certain on-site study visits may be replaced by telemedicine visits (a remote visit that is done by video or phone call).
- b. The run-in start visit should generally be 1 week after the screening visit (with a recommended window of +/- 4 days). Subjects who at screening may require testing of pancreatic autoimmunity (ie, GAD-65 and/or IA antibodies) or who require a repeat of other screening procedures may have the duration of the screening period and/or run-in period increased by 1 to 2 weeks to allow sufficient time for the assessments to be obtained.
- c. Subjects who have a Week 12 HbA₁c of ≥7.0% and eGFR ≥60 mL/min/1.73m² will be re-randomized to either remain on double-blind canagliflozin 100 mg (or matching placebo) or to up-titrate to double-blind canagliflozin 300 mg (or matching placebo). See Section 9.1.4.3, Re-randomization.
- d. Early withdrawal visit evaluations will be performed in subjects who prematurely discontinue study drug (see Section 10.2, Study Drug Treatment Premature Discontinuation, Reinstitution, and Follow-up) and in subjects who withdraw consent from the study (either on their own and/or by their parents[s]/legal guardian[s]). See Section 10.3, Withdrawal from the Study). The early withdrawal visit evaluation should be performed as soon as possible after the last dose of study drug is taken.
- e. A telephone follow-up contact (or optional study visit, at the discretion of the investigator) will be conducted for all subjects approximately 30 days after the last dose of study drug to collect serious adverse events and adverse events of interest since the last visit unless the subject has died, has been lost to follow-up, or has withdrawn consent. If a telephone contact or study visit is not possible, follow-up information may be collected via email or other electronic means. This follow-up is not required in subjects who discontinue study drug prematurely and continue to attend all subsequent study visits. At this telephone contact, investigators should ask subjects about any foot problems and remind them about routine preventative foot care and early intervention for foot problems.
- f. The informed consent form for the parent(s)/legal guardian(s) (and the assent form for minor subjects, as described in Section 16.2.3, Informed Consent/Pediatric Assent) must be signed before any study procedure is performed.
- g. Inclusion/Exclusion criteria must be reviewed at all visits up to and including the baseline visit/Day 1. Eligibility cannot be confirmed until the results of screening procedures and all screening laboratory test results are returned and reviewed.
- h. Record any medications taken from up to 30 days before screening (and up to 6 months before screening for AHAs) until the first dose of double-blind study drug on Day 1 (baseline) as prestudy therapy in the corresponding eCRF.
- i. Concomitant therapy includes all medications since the first dose of study drug on Day 1; after study drug discontinuation, use of AHA therapies will be recorded at the final visit or contact.
- j. Eligibility for re-randomization will be based on HbA1c and eGFR values obtained at Week 12. At this visit sites should schedule appointment for Week 13 for ALL subjects and confirm or cancel by phone upon review of laboratory results.
- k. Only those subjects who qualify for re-randomization will return to the site at Week 13 where the site personnel will dispense new bottles of study drug and provide new dosing instructions. Subjects not undergoing re-randomization will not return to the site at Week 13.
- 1. See Section 6.2.2, Glycemic Rescue Therapy: Criteria and Implementation, for additional details for subjects meeting the protocol-specified glycemic rescue criteria.
- m. Three consecutive blood pressure readings will be taken. (see Attachment 3, Method of Blood Pressure Measurement). Pulse rate will be measured once after subject has been sitting for at least 5 minutes at each clinic visit.
- n. Whenever possible, body weight will be measured using the same calibrated scale at each visit. Subjects will be weighed at approximately the same time of day on the same scale wearing underwear and a gown and without shoes. **Note**: if disrobing for weighing is logistically impossible, the subject must be dressed as lightly as possible, with consistency from visit to visit. Subjects will be instructed to empty their bladders before being weighed.
- o. Height will be measured using a stadiometer. (see Attachment 5, Guideline for Collecting Height Measurements).
- p. See Attachment 6: Tanner Staging for guidance on Tanner Staging. Note: once subjects have reached Stage 5, no later assessments are required.
- q. Physical examinations will include a review of body systems (head and neck, eyes, chest and lungs, cardiovascular, extremities and back, and abdomen examination). Significant findings that are present must be documented in the source and eCRF.
- r. Subjects should be counseled to maintain a diet and exercise regimen consistent with those outlined in treatment guidelines for T2DM (eg, the American Diabetes Association guideline). Subjects will receive information regarding the signs and symptoms of and treatment for hypoglycemia (see Attachment 4, Hypoglycemia: Definitions, Symptoms, and Treatment) and the signs and symptoms of DKA (see Attachment 1, Instructions on Ketone Monitoring and Sick Day Management).
- s. Subjects will be instructed to return with their completed diaries to the study site for review by study-site personnel at each clinic visit (eg, for review of hypoglycemic events, insulin dosage changes [only for subjects who are on insulin], self-monitoring of blood glucose values, ketone levels, concomitant medications, timing of study drug taken and any missed doses of study drug).

- t. Hypoglycemic episodes should be recorded on the hypoglycemia eCRF and also on the adverse event eCRF if considered as an adverse event by the investigator (see Attachment 4 Hypoglycemia: Definitions, Symptoms, and Treatment).
- u. Subjects will be provided with and instructed on the use of a home blood glucose/ ketone monitoring system. Subjects will also be instructed on how to measure urine ketones (to be only used as a back-up procedure in case capillary ketones cannot be assessed). Blood glucose and blood and urine ketone testing supplies will also be provided as necessary.
- v. Consistent with standard diabetes treatment guidelines, all study participants should be provided with routine preventative foot care and early intervention for foot problems (see Section 12.2.1, All Adverse Events for further detail).
- w. Adverse events will be monitored throughout the study from the time of signing the informed consent form until the end of the study (see Section 12.2.1, All Adverse Events).
- x. Specific details about specimen collection, storage, packaging, and shipping will be provided in the laboratory manual. For FPG, fasting C-peptide, and lipids, subjects must be fasting for at least 8 hours before blood sample collection, except for the screening visit when non-fasting blood samples may be collected. A set of plasma, serum, and urine samples will be collected at each specified time point. The urine collections for routine urinalyses and exploratory specimens should be obtained from a spot urine specimen in the clinic.
- y. Hematology and serum chemistry are performed at the screening visit and should not be repeated at baseline, unless the screening visit was performed more than 4 weeks before the baseline visit. No fasting lipid panel will be collected at the Screening Visit; please ensure to collect fasting lipid panel at the Baseline visit/Day 1.
- z. Serum (β-human chorionic gonadotropin [β-hCG] pregnancy testing will be performed for all female subjects of childbearing potential at the screening visit. Additional urine (or serum) pregnancy tests may be conducted throughout the study in sufficient number, as determined by the investigator or required by local regulations, to establish the absence of pregnancy during the study. Serum pregnancy test must be performed and the result reviewed before randomization.
- aa. The urine sample for albumin/creatinine ratio should not be collected if the subject is menstruating, has exercised vigorously in the past 24 hours, or had a fever or an active infection within the past 2 days of the clinic visit.
- bb. Subjects will be given urine collection containers at each of the clinic visits preceding the first morning urine collection time points. The subject will provide a urine specimen from the first morning void on the morning of the clinic visit. If the subject does not provide the morning void collection on the day of the visit, the subject may bring a first morning void specimen to the investigational site during the subsequent week. For subjects who have atypical sleep patterns, the collection should be made at the end of the subject's usual sleep period. Study research staff is encouraged to contact the subject before this clinic visit as a reminder to the subject that he/she will need to provide a urine specimen at a particular visit (only 1 urine specimen is necessary at the indicated visit for the determination of albumin/creatinine ratio).
- cc. If the first morning void on Week -2 visit shows a presence of proteinuria (ie, proteinuria +1 and above) based on the central laboratory urine dipstick, 24-hour urine collection will be done during the run-in period. Subjects who require a 24-hour urine collection prior to randomization, will also be required to provide a 24-hour urine sample on Week 26 and Week 52. Subjects who had a Week -2 first morning void negative for protein and develop a positive first morning void after randomization are not required to obtain 24-hour urine samples. Instead, in these subjects first morning urine sample will be collected for the remainder of the study.
- dd. Only required in subjects with no documented history of absence of pancreatic autoimmunity.
- ee. Subjects will be instructed to refrain from taking the study drug the morning of the clinic visit. The subject will be instructed to take the dose of study drug before the subject's next meal, after the study visit. The subject will record the time that the study drug was taken on the day preceding the clinic visit. Refer to laboratory manual for further information regarding the collection, handling, shipment and labeling of pharmacokinetic samples.

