All subjects, regardless of their study completion status, will have a follow-up telephone contact (or optional study visit, at the discretion of the investigator) approximately 30 days after their last dose of study drug is taken to collect information on any serious adverse events and adverse events of interest.

Subjects who discontinue the study during the double-blind treatment phase will not be replaced.

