Subjects who prematurely discontinue study drug will require an immediate EOT assessment (either on the day of study drug discontinuation or as soon as possible following study drug discontinuation). It is the intent that subjects who discontinue study drug will continue in the study according to the visit schedule described in the Time & Events Schedule. After early discontinuation of study drug, subjects will continue to be followed up for specific data collection, including vital signs, body weight, laboratory assessments, serious adverse events, adverse events of interest, and adverse events of special interest for the duration of the study. See Section 10.2.4, Comprehensive Follow-up at Scheduled Study Visits Following Premature Discontinuation of Study Drug, for more detail. (Refer to Section 12, Adverse Event Reporting for a list of adverse events of special interest that will be collected). All subjects, regardless of their completion status, will have a follow-up telephone contact (or optional study visit, at the discretion of the investigator) approximately 30 days after their last dose of study drug is taken to collect information on any serious adverse events and adverse events of interest.

Subjects who discontinue the study during the double-blind treatment phase will not be replaced.

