## 9.1.5. Post-treatment Phase (Follow-Up)

All subjects should have a follow-up telephone contact (or optional study visit, at the discretion of the investigator) approximately 30 days after the last dose of study drug to collect any serious adverse events and adverse events of interest that occurred since the last visit, unless the subject has been lost to follow-up, has withdrawn consent, or has died. If serious adverse events are

obtained via telephone contact, written documentation of the communication must be available for review in the source documents. If the subject has died, the date and cause of death will be collected and documented on the eCRF.

All subjects who discontinue study drug prematurely should continue to attend all subsequent study visits in the same way as the subjects who are still on the study drug treatment, unless the subject (and/or the parents[s]/legal guardian[s]) has elected to withdraw his/her consent from the study.

Subjects who discontinue study drug early for any reason (other than withdrawal of consent for follow-up contacts) will be contacted according to the post-treatment visit (or more frequently if necessary based on the investigator's knowledge of the subject) until completion of the overall study, with the goal of collecting any information on vital signs, body weight, laboratory assessments, serious adverse events, adverse events of interest, and adverse events of special interest. See Section 10.2.4, Comprehensive Follow-up at Scheduled Study Visits Following Premature Discontinuation of Study Drug, for more detail.

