# 10.2.2. EOT and 30-Day Follow-up Assessments for Subjects Who Prematurely Discontinue Study Drug

If a subject discontinues study drug for any reason before the end of the 52-week double-blind phase, EOT and 30-day post-treatment follow-up assessments should be obtained and scheduled assessments should be continued.

Subjects who prematurely discontinue study drug will require an immediate EOT assessment (either on the day of study drug discontinuation or as soon as possible following study drug discontinuation) as well as an off-drug follow-up assessment (ie, clinic visit or telephone contact) approximately 30 days after their last dose of study drug. The Time and Events Schedule describes the evaluation required. If for some reason the subject is unable to be seen within 30 days after discontinuing study drug, the EOT visit may be omitted, but a 30-day off-drug follow-up assessment should be performed.

If a subject discontinues from study drug prior to Week 52, he or she will be followed as per the assessments included in the Time and Events Schedule (see Section 10.2.4, Comprehensive Follow-up at Scheduled Study Visits Following Premature Discontinuation of Study Drug, for more detail).

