#### 12.2. **Procedures**

#### 12.2.1. **All Adverse Events**

All adverse events and special reporting situations, whether serious or non-serious, will be reported from the time a signed and dated ICF is obtained until completion of the study (including subjects who discontinue study drug treatment).

Data will be collected in source documents and on the eCRF for all adverse events.

All deaths will also be recorded.

For adverse events of interest (see Section 9.8, Safety Evaluations) a supplemental eCRF will be used to collect additional information. Investigators may be asked to provide additional information on adverse events, based upon review by the MSRC or the IDMC.

CONFIDENTIAL – FOIA Exemptions Apply in U.S.

Serious adverse events, including those spontaneously reported to the investigator within 30 days after the last dose of study drug, must be reported using the Serious Adverse Event Form, which must be completed and signed by a member of the study-site personnel, and transmitted to the sponsor within 24 hours. The sponsor will evaluate any safety information that is spontaneously reported by an investigator beyond the time frame specified in the protocol.

All events that meet the definition of a serious adverse event will be reported as serious adverse events, regardless of whether they are protocol-specific assessments.

All adverse events, regardless of seriousness, severity, or presumed relationship to study drug, must be recorded using medical terminology in the source document and the eCRF. Whenever possible, diagnoses should be given when signs and symptoms are due to a common etiology (eg, cough, runny nose, sneezing, sore throat, and head congestion should be reported as "upper respiratory infection"). Investigators must record in the eCRF their opinion concerning the relationship of the adverse event to study therapy. All measures required for adverse event management must be recorded in the source document and reported according to sponsor instructions.

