6.1. Adverse Events

Adverse events will be summarized for the 26-week core double-blind treatment period and for the 52-week double-blind treatment phase separately. AEs will be coded using the latest version of the Medical Dictionary for Regulatory Activities (MedDRA) at the time of database lock. Therefore, the preferred terms presented in Attachment 2 may be updated to reflect such updates. A treatment-emergent AE (TEAE) is defined as an adverse event with an onset after the initiation of double-blind study medication and before the last study medication date + 30 days. AEs with a start date prior to initiation of double-blind study medication which are subsequently reported to have either an increase in intensity or change in attribution in relationship to study medication (ie, no attribution to possible, probably, very likely) after the initiation of double-blind study medication will also be considered as TEAEs. Treatment-emergent AEs before the initiation of rescue therapy and TEAEs regardless of rescue therapy will be summarized separately for the 26-week core double-blind treatment period and for the 52-week double-blind treatment phase.

The overall incidence (ie, number and percent of subjects with one or more AE in each category) of AEs, AEs leading to discontinuation of study medication, drug-related AEs, drug-related AEs leading to discontinuation of study medication, serious AEs, serious AEs leading to discontinuation of study medication, serious drug-related AEs, serious drug-related AEs leading to discontinuation of study medication, serious drug-related AEs, serious drug-related AEs leading to discontinuation of study medication, serious drug-related AEs, serious drug-related AEs leading to discontinuation of study medication and deaths, will be summarized by treatment group.

AEs by SOC (ie, number and proportion of subjects with one or more AEs within a SOC) will be summarized by treatment group.

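### The protocol contradicts itself on who receives the 30-day post-dose safety contact, and that contact asks for fewer event types than the SAP's treatment-emergent window counts

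*Protocol*

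**What the plan says.** **Who receives the contact.** Footnote e of the Time and Events Schedule sets a contact about 30 days after last dose for all subjects other than those who died, were lost or withdrew consent. It then makes an exception: "This follow-up is not required in subjects who discontinue study drug prematurely and continue to attend all subsequent study visits". Section 10.1 likewise drops the follow-up after Week 52 for early discontinuers.

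Section 10.2.2 says of subjects who stop study drug early that "EOT and 30-day post-treatment follow-up assessments should be obtained and scheduled assessments should be continued". It repeats that they need an immediate end-of-treatment assessment "as well as an off-drug follow-up assessment (ie, clinic visit or telephone contact) approximately 30 days after their last dose of study drug". Section 3.1 states: "All subjects, regardless of their completion status, will have a follow-up telephone contact". The Synopsis says the same ("All subjects, regardless of their study completion status, will have a follow-up telephone contact"), and Section 9.1.5 excepts only death, loss to follow-up and withdrawn consent.

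**Which events are asked for.** Section 9.1.5 gives the purpose of the contact as "to collect any serious adverse events and adverse events of interest that occurred since the last visit". Footnote e, the Synopsis and Section 3.1 set the same limit. Section 12.2.1 requires all adverse events, serious or not, to be reported "until completion of the study (including subjects who discontinue study drug treatment").

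**Which events are counted.** SAP 6.1 treats any event as treatment-emergent if it starts after first dose and "before the last study medication date + 30 days". SAP 6.1.2 applies this rule to hypoglycemia. Protocol Section 11.6 instead ties treatment-emergent events to onset in the treatment phase and mentions no 30-day extension.

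**The concern.** A site cannot follow both footnote e and Section 10.2.2. Section 10.2.2 asks for the contact and for continued visits together, so it covers exactly the group that footnote e exempts.

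The SAP's window also reaches past the point where all events are actively asked for. SAP 6.1.1 and its Attachment 2 analyse vulvovaginal candidiasis, balanitis, urinary tract infection and volume depletion. In their non-serious forms, none of these is among the events of interest or of special interest in Protocol Section 12. An event of this kind starting two weeks after a completer's last dose is treatment-emergent under the SAP, yet the only remaining contact does not ask about it.

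Overall safety and tolerability is a primary objective, so completeness of treatment-emergent counts matters.

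**Working it through.** The plan states no figure to reproduce. The check compares the 30-day window with the visit schedule.

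**Inputs.** Target days from SAP Table 1 are 1 (baseline), 43, 85, 141, 183 (Week 26), 239, 295 (Week 42) and 365 (Week 52). The window closes at last dose + 30 days (SAP 6.1).

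**Step 1, visit gaps.** Differences between successive target days are 42, 42, 56, 42, 56, 56 and 70 days. All exceed 30, so no clinic visit is guaranteed to fall inside the window.

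**Step 2, early discontinuer who keeps attending, no contact made.** With last dose on day L and next visit on day V, the visit comes V − (L + 30) days after the window closes. For a stop on a visit day:

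| Last dose | Next visit | Delay after window closes |
|---|---|---|
| Day 183 | Day 239 | 239 − 213 = 26 days |
| Day 239 | Day 295 | 295 − 269 = 26 days |
| Day 295 | Day 365 | 365 − 325 = 40 days |

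The ±7-day visit allowance lets the 70-day gap run from 56 to 84 days. A stop between visits can put a visit inside the window. The first question then comes sooner, and the rest of the window is covered at the following visit.

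**Step 3, early discontinuer near the end of the study.** The Week 52 visit lies fewer than 30 days after last dose when L > 365 − 30 = 335. For L = 350, as an example, the window runs to Day 380, leaving 380 − 365 = 15 days after the last visit. Under footnote e and Section 10.1 nobody is due to ask about those days. Under Section 10.2.2 the contact is made, but only for the restricted list.

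**Step 4, completer.** With last dose at Day 365, the window runs to Day 395. Only the restricted contact covers those 30 days, which are 30/395 = 7.6% of the window by calendar time. This is a share of time, not of events.

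**Step 5, event scope.** At scheduled visits, footnote w and Section 12.2.1 require adverse events without restriction. At the 30-day contact the restriction is explicit. The gap therefore belongs to the contact, not to the visits.

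**The case against.** The strongest reply is that the exempted group is not lost. The exemption applies only to subjects who attend every later visit. Adverse events are recorded without restriction at those visits, Section 9.1.5 has these subjects attend as if still on drug, and Section 12.2.1 names drug discontinuers expressly. An event 20 days off drug is asked about at the next visit, with a recall interval no longer than the ordinary visit gap. This stands: for most of the group the consequence is delayed recall, not missing data.

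Section 10.2.4 might be read as restricting the events collected at scheduled visits after early discontinuation. That reading is weak. The section calls collection comprehensive, refers to the Time and Events Schedule, and presents its list as inclusive. Its alternate follow-up text asks for adverse events without restriction.

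Two mitigations also count. Protocol Section 11.6 provides a summary of all reported events whether or not treatment-emergent, and Section 12.2.1 requires a check for volume depletion at every visit. Neither reaches a completer's last 30 days unless the subject volunteers the event or an optional visit is held.

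Finally, Section 10.1 agrees with footnote e. It conflicts with Section 10.2.2 only when the 30-day contact would fall after Week 52, that is, for stops after about Day 335.

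**Conclusion.** The point holds as an internal contradiction about who receives the contact, together with a mismatch between what the contact collects and what the SAP counts. The events not systematically asked for are non-serious events outside the listed categories, in the 30 days after a completer's last dose and in the part of the window beyond Week 52 for subjects stopping after about Day 335. Other early discontinuers who keep attending give these events by later recall. The delay of 26 to 40 days assumes visits on target days and a stop on a visit day from Week 26 on.

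Two stronger readings are tempting and unsupported:

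- **A bias against one arm.** A reader might infer that loss is greatest in the arm with more early stopping. But early discontinuers who stay in the study have later visits with unrestricted recording, while completers have only the restricted contact. More early stopping with retention could mean fuller capture. No direction follows from the documents.
- **A number of subjects.** Applying the 10% inflation factor to 73 per arm gives 0.10 × 73 = 7.3. That factor allows for leaving the study, whereas the exempted subjects stop drug and stay. No drug-discontinuation rate is given, so no count can be derived.

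The result is incomplete and uneven ascertainment of treatment-emergent events. It is a minor point that does not touch the primary HbA1c analysis.

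**What to change.** 1. Reconcile footnote e, the Synopsis, and Sections 3.1, 9.1.5, 10.1 and 10.2.2 so that they give one rule on who receives the 30-day contact, including subjects whose last dose falls within 30 days before Week 52. Which rule to adopt is for the sponsor.
2. Match the events asked for to the events counted. Either record all adverse events to last dose + 30 days in every subject, or limit the SAP's post-dose window to the event types actually collected in it. The contact text should also say whether it covers the events of special interest in Section 12, which it does not now name.
3. Use one definition of treatment-emergent in Protocol Section 11.6 and SAP 6.1, carried through to hypoglycemia in SAP 6.1.2.

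The cost is wording in both documents and, under the first option in item 2, a slightly longer call. No added clinic visit or sample-size change is needed.
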